4.3.2 Radiation Therapy

Radiation therapy to the target tumor will be delivered with external beam radiation therapy. In metastatic cases where the intent is palliative, the dose of radiation will be 3750 cGy delivered in 15 daily fractions, 4-5 days a week. In locoregionally recurrent or progressive cases where the intent is to enhance locoregional control, the dose of radiation will be 5000 cGy delivered in 25 fractions, 4-5 days a week plus an optional 10-14 Gy boost to areas of gross tumor. In cases where patients have had prior radiation and there is overlap between current and prior fields, normal tissue constraints will be followed as per departmental guidelines.

Radiation therapy will not be delivered on holidays for which the Department of Radiation Oncology is closed. When radiation treatment is missed because of a holiday or unforeseen circumstances, the missed dose will be made up at the end of RT.

5.1 THERAPEUTIC/DIAGNOSTIC AGENTS

5.2 Cisplatin Availability, Preparation and Storage

Commercially available cisplatin injection (1 mg/ml): Each ml of sterile, unpreserved solution contains 1mg of cisplatin with 9mg of sodium chloride and 1mg of mannitol in water for injection. Hydrochloric acid is added to adjust the pH. Single-dose glass vials of 10 and 50 ml contain 10 and 50 mg of cisplatin, respectively. None of the injection components such as IV needles, syringes and sets should have aluminum components, because aluminum is incompatible with cisplatin. A black precipitate forms (platinum) when exposed to aluminum and loss of potency will occur. Vials of cisplatin injection, USP, are stored at room temperature between 15-25 degrees Celsius. Please refer to the FDA-approved package insert for complete product information.

5.3 Tumor Biopsy

4 cores biopsies are required, with 2 optional cores, will be obtained from the tumor to be irradiated, with image-guidance as necessary. The safety and feasibility of the biopsy will be determined by the study Interventional Radiologist. Clip placement in target lesion is recommended if CT or MR-guided biopsy is performed. Skin metastases will be biopsied by an MSKCC surgeon, dermatologist or a radiation oncologist. The minimum core length is 6 mm. One out of the 4 cores will be fixed in 10% neutral buffered formalin and sent to Pathology for routine diagnostic confirmation of triple negative breast cancer, prior to irradiation. The remainder of the cores will be placed in a 1 mL freezer vial in DMEM standard medium at room temperature with regular ice on top of the specimens and transported directly to [name] laboratory for the MSK-HRR assay. If there is any remaining tissue left after the MSK-HRR assay, DNA will be extracted and stored in [name] lab for possible future analysis. The estimated turn-around time for functional assay, from receipt of tissue to interpretation, is 5 business days. However, the results of the assay (determining HR-proficient vs HR-deficient) status are not necessary for patients in order to receive the study treatment and will only be shared with the study statistician and primary investigator, for the purposes of confirming which patients can remain on study (i.e. they must have a definitive HRR repair status). Patients who are unable to obtain a definitive HRR status will be excluded from analysis of the primary endpoint of the study, but will be counted towards the secondary and exploratory objectives of the study.

5.4 MSK-HRR Assay

The specimens will be transported to the Laboratory of Molecular Radiation Biology in the Zuckerman Research Building, Room 419, led by [name] and managed by [name]. The time from tumor harvest to initiation of laboratory processing should ideally not exceed 2 hours. Tumor specimens will be divided into 2 separate and equally sized parts; one part will be irradiated to 10 Gy (gamma-rays from the Shepard Mark-I ¹³⁷Cs irradiator, Model 68, SN643), in the SKI Radiation Core Facility and the second part will be sham-treated. Following irradiation or sham treatment, the specimens will be incubated in humidified cell culture incubators at 37°C with 5% CO₂ for 4 hours. One part of each specimen will then be snap-frozen in optimal cutting temperature (OCT) compound (Sigma-Aldrich), with a view to preparing histological sections in the Molecular Cytology Core Facility

(MCCF). Tumor will be snap frozen in optimal cutting temperature compound and stored at -80°C. RNA was extracted using standard Trizol extraction. The DNeasy kit (Qiagen, Valencia, CA) was used to isolate genomic DNA. The quality of the DNA was verified on a 1% agarose gel. RNA quality was assessed using the Agilent Bioanalyzer 2100.

Hematoxylin and eosin staining of representative sections will also be performed by the MCCF. The second part will be disaggregated by scalpel mincing, with or without collagenase, to develop a cell suspension which can be used in a cytocentrifuge followed by formaldehyde fixation and cytologic analysis. Thin sections or cytocentrifuge preparations will be stained using the published immunofluorescence protocols. Immunofluorescence microscopy will be carried out in the Laboratory of Molecular Radiation Biology on a confocal microscope. Briefly, cryoslices or cytocentrifuge slides will be fixed and permeabilized, then blocked and probed with anti-RAD51, anti-BRCA1, and anti-FANCD2 antibodies. Slides will then be washed and incubated with fluorescently labeled secondary antibodies. Images will be captured and subnuclear foci will then be quantified.

Cell nuclei will be analyzed for subnuclear foci formation of phosphohistone H2AX (γ H2AX), BRCA1, and RAD51 in both the irradiated and non-irradiated states using a Zeiss LSM 510 confocal microscope. In order to quantify foci formation, over 200 nuclei will be counted for both the irradiated and non-irradiated conditions. A nucleus will be scored as positive if it contains greater than 5 foci. The formation of γ H2AX foci is an upstream event in the DNA damage response and indicates the presence of a double strand break [66]. γ H2AX staining will be used as a control for cell viability at the time of fixation and adequacy of the staining procedures. In addition, the mean number of positive BRCA1 and RAD51 nuclei for each condition will be quantified as a function of the percent of nuclei with γ H2AX foci following IR in order to normalize for differences in cell viability across various tumor specimens.

Comparative genomic hybridization (CGH) will be performed at the Genomics Core Laboratory at Memorial Sloan-Kettering Cancer Center by cy5 labeling tumor DNA to 1M aCGH human microarrays from Agilent (Santa Clara, CA) with cy3 labeled genomic DNA from Roche (Indianapolis, IN). The arrays will be scanned with Agilent high-resolution microarray scanner (G2538C). Data will be extracted with Agilent feature extraction software (v10.7). Data analysis will be performed using the RAE algorithm [67].

Any remaining tissue from the tumor biopsies will be flash frozen in liquid nitrogen and stored at -80°C and banked in [name] lab for future analyses, including BRCA promotor methylation status.

If BRCA status is not known at the time of study registration, patients will either be referred to the MSKCC Genetics department for evaluation of BRCA status, or this information may be obtained from analysis of the fresh tumor biopsy in [name] laboratory.

5.5 Immune Correlates

In order to evaluate the association between intratumoral and stromal lymphocytes and response to treatment [65-67], the pre-treatment tumor biopsy slides (formalin fixed paraffin embedded, FFPE) will be reviewed by the two study pathologists, using the standardized methodology for evaluating TILs based on H&E sections of core biopsies [68]. Intratumoral lymphocytes are defined as intraepithelial

mononuclear cells within tumor cell nests or in direct contact with tumor cells and will be reported as the percentage of the tumor epithelial nests that contain infiltrating lymphocytes [65]. Stromal lymphocytes are defined as the percentage of tumor stroma area that contains a lymphocytic infiltrate without direct contact to tumor cells. In addition, immunohistochemical analyses including but not limited to CD3, CD4, CD8, FOXP3 and CD20 will be performed in order to further characterize TILs.

Peripheral blood will be drawn before treatment and at two time points following completion of the cisplatin/RT to evaluate epitope spreading by seromic analysis for tumor-associated antigens. In addition, the peripheral blood mononuclear cells will also be preserved for evaluation of T cell immunophenotyping. Immunophenotyping will be determined using flow cytometry to determine the effect on individual lymphocyte subsets in peripheral blood mononuclear cells (PBMC). Flow cytometric assessment of the lymphocyte subsets CD4⁺, CD8⁺, CD16⁺, CD19⁺ and CD56⁺ will be examined as percent and absolute number. FOXP3⁺ and FOXP3⁻ lymphocytes with the following markers will also include but not limited to: CD4⁺, CD25, CD45RA, CD45RO, LAG3, GARP, PD1, and CTLA4. Activation markers such as CD44 and CD69 will also be examined. The blood samples will be delivered to the Immune Monitoring Core Facility where the processing and storage will occur. The IMF may also perform ELISPOT, flow tetramer staining, and/or intracellular polyfunctional cytokine staining, TCR V β Repertoire analysis and Spectratyping to further characterize tumor-antigen specific CD4⁺ and CD8⁺ T cell response before and after treatment. PBMCs will be archived for all patients to support complete analysis of the profile. Archived serum may also be assayed for levels of chemokines, cytokines, and tumor-associated soluble proteins by techniques that may include but are not limited to, ELISA or multiplex assays. Analyses may include markers of inflammation, immune activation, host tumor growth factors, and tumor-derived proteins. These assays will also take place in the Immune Monitoring Facility (IMF).

6.1 CRITERIA FOR SUBJECT ELIGIBILITY

6.2 Subject Inclusion Criteria

- Histologically-confirmed invasive triple negative breast cancer (ER <1%, PR <1%, her-2-neu 0-1+ by IHC or FISH-negative) or as determined by MD discretion
- Radiation to the recurrent or metastatic site is clinically indicated and would be considered standard care for palliation or for locoregional control
- Age \geq 18 years
- Tumor to be irradiated is measurable by RECIST 1.1 or PRC (see Appendix 1 and Section 12.0)
- Willingness to undergo tumor biopsy prior to initiation of treatment
- Life expectancy greater than 6 months
- ECOG performance status 0-2
- Any prior chemotherapy is allowed including prior treatment with platinum-containing chemotherapy
- Prior treatment with FDA-approved or investigational biologics or novel molecularly target therapies, including oral or IV formulations, are permitted. Patients must be off prior targeted therapy for at least 14 days prior to study biopsy.

- Use of an effective means of contraception in women of child-bearing potential
- Ability to comprehend and sign informed consent
- Adequate organ and marrow function within 14 days prior to study entry, defined as:
 - Absolute neutrophil count (ANC)>1000/mm³
 - Hemoglobin >9 gm/dl
 - Platelets >100,000/mm³
 - Serum creatinine <1.5 mg/dl OR creatinine clearance of \geq 50 cc/min
 - SGOT/SGPT<2.5X institutional ULN (<5X ULN if known liver metastases)

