4.3 Intervention

4.3.1 Cisplatin Administration

Cisplatin treatment should be initiated following study registration. The starting dose of cisplatin is established as 25 mg/m² ivpb once a week (\pm 3 days) for 1-2 weeks prior to radiation. Dose modification following the first dose of cisplatin is subject to the discretion of the treating physician. Dosing calculation guidelines will follow MSKCC policies described on the website:

http://mskweb5.mskcc.org/intranet/shared/pharmacy/guidelines/Chemo_Guidelines/Manuals/Cisplatin.html

Cisplatin may be initiated immediately following simulation but prior to first radiation fraction. The rationale is so that the patient may initiate a form of treatment while waiting 1-2 weeks for radiation treatment planning to be completed.

Cisplatin may cause myelosuppression or other known non-hematologic toxicities. Following the completion of RT, pending no toxicities, but prior to the week 12 post RT evaluable timepoint, patients will continue to receive cisplatin based on MD discretion, or until POD.

The starting (first) dose of cisplatin will be 25 mg/m² ivpb once a week (\pm 3 days). Following the first dose of cisplatin, a CBC will be drawn once a week (\pm 3 days) prior to treatment to ensure treatment parameters are met. A comprehensive panel and Mg++ level will be obtained on D15 (\pm 3 days) of every cycle of cisplatin; these values will inform the dose for the following cycle of cisplatin. The length of one cycle of Cisplatin is 21 days. If cisplatin is withheld, the cycle count for treatment is also held. Based on the laboratory values drawn from the prior week's bloodwork, if the following parameters are met, cisplatin should be held as directed.

- If ANC is <1,000 mcL and/or platelets are <100,000 mcL, withhold cisplatin therapy for one week and repeat measurements. Physicians have the option of administering growth factor support during the time when ANC < 1,000 mcL or platelets are < 100,000 mcL. The treating MD may modify the subsequent cisplatin doses at their discretion. If there is a delay of 3 consecutive weeks of treatment due to toxicity, then the patient must discontinue protocol therapy and be removed from the study.
- If the ANC is still <1,000 mcL or platelets are 75,000-99,000 mcL, then hold weekly cisplatin again until the ANC is >1,000 mcL and platelets are >100,000 mcL. The treating MD may modify the subsequent cisplatin doses at their discretion.

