- If serum creatinine is >1.5 mg/dL, delay treatment, provide intravenous hydration and check 12 or 24 hour creatinine clearance, serum creatinine and electrolytes after 24 hours. If the serum

creatinine is ≤ 1.5 mg/dL and creatinine clearance ≥ 60 cc/min, may give full dose of cisplatin. If serum creatinine is 1.6-1.9 and creatinine clearance is between 30-60 cc/min, cisplatin can be given at the discretion of the treating physician. If serum creatinine is >2 OR creatinine clearance is <30 cc/min, hold cisplatin.

- If the patient develops any non-hematologic grade 3-4 toxicity, cisplatin will be held until toxicity is reduced to grade 2 or less. Dose reduction is permitted at the discretion of the treating physician. If a patient experiences grade 2 toxicity (with exception of alopecia) that lasts >2 weeks, cisplatin will be held and dose reduction recommended at discretion of the treating physician. Cisplatin will be discontinued if greater than grade 2 toxicity persists following 2 dose reductions.
- If the patient develops an intercurrent illness (e.g. infection) that, in the opinion of the treating medical oncologist, mandates a delay of cisplatin therapy, the intercurrent illness must be resolved within a time frame such that no more than 2 weekly doses of cisplatin are withheld. If therapy must be withheld for a longer period of time, the patient will be removed from the study.
- Following the completion of RT but prior to the week 12 post RT evaluable timepoint, patients will continue receiving cisplatin based on MD discretion. The dose and schedule of cisplatin after the completion of RT will be at the discretion of the treating MD. If there is a delay of 3 consecutive weeks of treatment, then the patient must discontinue protocol therapy and will be removed from study. Continuation of cisplatin and the dose and schedule of cisplatin after Week 12 post RT assessment will be at the discretion of the treating MD.
- Note: Disruption to the cisplatin treatment schedule for 3 weeks due to unforeseen circumstances, holidays or the patient being on vacation is permitted and will be reviewed on a case-by-case basis.

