6.3 Subject Exclusion Criteria

- Unmeasurable target tumor site by RECIST 1.1 or PRC (ex: lesions <2 cm on CT or MR scan, leptomeningeal disease, ascites, pleural/pericardial effusion, lymphangitis, non-FDG-avid skin lesions)
- Brain metastases requiring focal or whole brain radiation will be excluded, as these lesions cannot be biopsied and can have life expectancies <6 months.
- Inability to obtain a biopsy of the tumor as deemed by the study Interventional Radiologist
- Prior chemotherapy completed <7 days prior to planned study entry
- Prior RT is allowed and must have been completed more than 7 days before planned study entry.

Note: For re-irradiation cases, standard departmental guidelines should be followed so as to not exceed normal tissue

- Life expectancy less than 6 months
- Intercurrent illness or other major medical condition or comorbid condition that might affect study participation (uncontrolled renal, pulmonary or hepatic dysfunction or infection)
- Renal dysfunction for which cisplatin dose would be considered unsafe.
- Women on study must be neither pregnant nor nursing nor expected to become pregnant during therapy. For premenopausal women, negative pregnancy test within 14 days of RT is required.
- Concurrent active malignancy other than non-melanomatous skin cancer or carcinoma in-situ of the cervix, unless treatment for the previous cancer was completed >2 years prior to study entry and patient has remained disease-free.

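### The renal entry line in Section 6.2 joins creatinine and clearance with OR, so it accepts values that meet the protocol's own cisplatin delay or hold wording in Section 4.3.1

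*Combined protocol and SAP*

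**What the plan says.** **Entry.** Section 6.2 lists, among the organ-function criteria to be met within 14 days before study entry, "Serum creatinine <1.5 mg/dl OR creatinine clearance of" at least 50 cc/min. Section 6.3 separately excludes "Renal dysfunction for which cisplatin dose would be considered unsafe", and it names uncontrolled renal dysfunction among the comorbid conditions that exclude a patient. Neither exclusion carries a number.

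**Dosing.** Section 4.3.1 introduces its rules by reference to the previous week's blood tests: "if the following parameters are met, cisplatin should be held as directed". The renal rule then runs in sequence:
- The opening step is "If serum creatinine is >1.5 mg/dL, delay treatment, provide intravenous hydration", with a timed clearance and repeat chemistry after 24 hours.
- If creatinine is then at most 1.5 and clearance at least 60, the physician "may give full dose of cisplatin".
- If "creatinine is 1.6-1.9 and creatinine clearance is between 30-60 cc/min, cisplatin can be given at the discretion of the treating physician".
- Finally, "If serum creatinine is >2 OR creatinine clearance is <30 cc/min, hold cisplatin".

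**Testing.** The pretreatment list in Section 8.1 and the table in Section 10.0 call for a metabolic panel with magnesium. Neither lists a creatinine clearance. On treatment, chemistry is scheduled on D15 of each 21-day cycle.

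**The concern.** The two sections combine the same two measurements in opposite directions. Entry passes on the better value, and the hold acts on the worse one. A patient can therefore satisfy the renal inclusion line with numbers that the dosing section says call for a delay or a hold.

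What is at stake is safety and consistent conduct. Section 11.2 describes cumulative nephrotoxicity as a major toxicity of cisplatin, and Section 6.2 allows prior platinum. Staff who apply the entry line literally and staff who read it together with 4.3.1 would reach different decisions on the same patient.

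**Working it through.** The plan gives no figure to reproduce here. The check is one of logic, with one illustration by arithmetic.

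**Step 1: write the rules as conditions.** Let S be serum creatinine (mg/dL) and C be clearance (cc/min).
- Entry line (6.2): S < 1.5 or C ≥ 50
- Delay, and the only written trigger for a clearance (4.3.1): S > 1.5
- Full dose after recheck (4.3.1): S ≤ 1.5 and C ≥ 60
- Discretion after recheck (4.3.1): S 1.6 to 1.9 and C 30 to 60
- Hold (4.3.1): S > 2 or C < 30

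**Step 2: apply them to value pairs,** assuming the values are unchanged at the recheck.

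| S | C | Entry line met by | Section 4.3.1 |
|---|---|---|---|
| 2.2 | 55 | clearance | delay, and hold |
| 2.0 | 55 | clearance | delay, then no later branch fits |
| 1.8 | 65 | clearance | delay, then no later branch fits |
| 1.7 | 55 | clearance | delay, then physician discretion |
| 1.4 | 28 | creatinine | hold wording met; no clearance triggered |
| 1.0 | 80 | both | neither delay nor hold |

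**Step 3: find the cause.** If both conditions had to be met, every accepted patient would have S < 1.5 and C ≥ 50. None of S > 1.5, S > 2 or C < 30 could then be true, so the overlap with delay and hold comes entirely from the OR. This locates the source and is not a proposal for the criterion.

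**Step 4: look for a scheduled step that would show a low clearance at normal creatinine.** Sections 8.1 and 10.0 list none. The 4.3.1 trigger needs S > 1.5, so a patient at 1.4 does not reach it. Footnote 7 to the Section 10.0 table gives cisplatin on D1, D8 and D15, while chemistry is scheduled on D15. Two doses can therefore precede the first scheduled on-treatment creatinine.

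**Step 5: ask whether such values are plausible.** The protocol names no formula for clearance. Assume the Cockcroft-Gault estimate for women, C = (140 − age) × kg × 0.85 / (72 × S):
- Age 75, 50 kg, S 1.4: 65 × 50 × 0.85 / 100.8 = 27.4
- Age 80, 50 kg, S 1.3: 60 × 50 × 0.85 / 93.6 = 27.2
- Age 70, 50 kg, S 1.4: 70 × 50 × 0.85 / 100.8 = 29.5
- Age 45, 80 kg, S 1.7: 95 × 80 × 0.85 / 122.4 = 52.8

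At 50 kg and S 1.4 the estimate reaches 30 when 140 − age = 30 × 100.8 / 42.5 = 71.2, that is, at about age 69. The low-clearance pattern thus needs an older, light patient with creatinine near the top of the accepted range. Section 6.2 sets no upper age limit. These profiles are chosen examples and give no frequency.

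**The case against.** Several points on the other side are sound and limit what can be claimed.

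- **Meeting the 6.2 line is not the same as being eligible.** A reader might infer that these patients are admitted. Section 6.3 excludes renal dysfunction that makes cisplatin unsafe, and a judgement-based exclusion is still an exclusion. This stands. The reply is only that the exclusion gives no threshold and requires no clearance value on which to judge.
- **A reader might infer that nothing would detect a low clearance.** That is too strong. Section 4.2 requires medical oncology assessment before enrolment and makes the starting dose depend on baseline laboratory results. Section 4.3.1 refers dose calculation to an institutional guideline whose content is not in the documents and which may require a clearance. What is missing is an explicit scheduled requirement in the protocol.
- **A reader might infer that creatinine 1.7 with clearance about 53 is eligible but untreatable.** It is not. After the delay and recheck, that pair falls in the discretion branch.
- **The reach of the dosing rules is uncertain.** They act on the prior week's blood tests, and the entry line uses values within 14 days before entry, so whether they govern dose 1 is not explicit. The clearance limb of the hold rule also closes a sequence opened by creatinine above 1.5, so whether it covers a normal creatinine is arguable. Both are ambiguities to settle, and they do not remove the overlap at creatinine above 2 with clearance of at least 50.
- **The illustration is not like for like.** Section 4.3.1 asks for a timed 12 or 24 hour clearance, and Step 5 uses a serum-based estimate. It shows plausibility only.
- **Entry limits and on-treatment limits may legitimately differ.** The documents do not support a demand for identical cut-offs in each section.

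**Conclusion.** The point holds as a conflict of wording that should be corrected. The renal inclusion line accepts three sets of values that the protocol's own dosing section acts against:
1. Creatinine above 2 with clearance of at least 50 meets the hold rule.
2. Creatinine above 1.5 and up to 2 with clearance of at least 50 meets the delay rule. Within this set, creatinine 1.6 to 1.9 with clearance up to 60 may then be treated at discretion, while the same creatinine with clearance above 60 fits no later branch.
3. Creatinine below 1.5 with clearance below 30 meets the hold wording, with no explicit scheduled step that requires the clearance.

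The first two sets follow from the text alone. The third also rests on reading the hold sentence as applying at any creatinine. The number of patients concerned cannot be estimated from the documents.

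A reader might infer damage to the week-12 response endpoint, through delays that lead to removal from the study. The documents do not support that. The renal step is a recheck after 24 hours, and nothing shows that these patients would reach a delay of 3 consecutive weeks. Section 14.0 also replaces patients who leave for reasons unrelated to disease. No sample size, power or analysis figure changes.

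**What to change.** - Reconcile Sections 6.2, 6.3 and 4.3.1 so that the entry line does not accept values that meet the protocol's own delay or hold rule.
- State how the creatinine and clearance conditions combine, and whether each section means a calculated or a timed clearance.
- State whether the 4.3.1 renal rules apply to the first dose and whether the clearance limb of the hold rule applies when creatinine is not raised. Settle what follows for value pairs that fit no branch.
- Record on the eligibility checklist, for every patient, a clearance calculated from the baseline creatinine already drawn, and name the formula.

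Which limits are right, and which passage should move, is for the sponsor's clinical team. The cost is amendment wording and one calculated value, with no new test. The downside is that a few patients with borderline renal function may be affected.
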